1.6 Study in Severe Covid-19 Pneumonia (CM4620-204)

A double-blind, randomized controlled study in patients with severe Covid-19 pneumonia, characterized by the need for low-flow or high-flow oxygenation and a P/F ratio ≤ 300 , is currently being conducted (CM4620-204). Part 1 of the study was a randomized open-label comparison of Auxora to standard of care. 30 patients were enrolled in Part 1, 26 patients receiving low-flow oxygen and 4 patients receiving high-flow oxygen. Of the 26 patients receiving low-flow oxygen, 17 patients were randomized to Auxora and 9 to standard of care. Of the 4 patients receiving high-flow oxygen, 3 were randomized to Auxora and 1 to standard

of care. Across both arms, 15 patients (75%) receiving Auxora had ≥ 1 AE and six patients (30%) had ≥ 1 SAE. Site investigators judged three AEs, each occurring in three different patients, as being related to the administration of Auxora: an episode of itching, an increase in alkaline phosphate, and a rash. They were all considered mild by the investigators and resolved. None of the reported SAEs were determined to be related to the administration of Auxora. Among patients receiving standard of care, eight (80%) had ≥ 1 AE and five (50%) had ≥ 1 SAE. There was no difference in AEs related to infections in the Auxora group when compared to standard of care (30% in each group). Two patients (10%) treated with Auxora and two patients (20%) receiving standard of care died while hospitalized between 10 and 17 days after randomization. Patients receiving low flow oxygen and treated with Auxora were noted to have a shorter median time to recovery, decreased need for invasive mechanical ventilation, and greater clinical improvement than patients receiving standard of care. A composite outcome of death or mechanical ventilation occurred less frequently in patients treated with Auxora.

Given the favorable safety profile and signals of efficacy, enrollment in the open-label study was halted, and the study was transitioned to Part 2 a double-blind RCT with matching placebo. The study is currently being conducted across multiple sites in the United States.

1.7 Rationale for Current Study and Selected Doses

The rationale for this study is to determine the optimal dose for use in patients with critical COVID-19 pneumonia based on pharmacodynamic markers obtained by BAL. Previous studies have randomized patients with severe COVID-19 pneumonia and acute pancreatitis with accompanying SIRS and hypoxemia who were not on a mechanical ventilator at the time of the initial infusion of Auxora. It remains necessary to determine if Auxora is an effective therapy in patients with a greater degree of diffuse alveolar damage and already requiring mechanical ventilation at the time of the initial infusion of Auxora. The selected dose may then be studied in patients with ARDS due to a variety of causes including bacterial pneumonia.

In the initial study of CM4620 in patients, CM4620-201, the low dose regimen provided the same C_{max} as the highest dose in the SAD and the total exposure in the MAD was compressed into 4 days instead of 7 days of dosing. In Cohort 4, male patients received a higher dose regimen that resulted in a 30% increase in total exposure without an increase in SAEs. PK modeling from plasma levels in CM4620-201 and CM4620-202, along with analysis of the time course of IL-6 decrease, lead to the decision to study 3 doses in CM4620-204. In Part 1, it appears that patients with initial P/F ratios less than 100 treated with Auxora may have benefited from additional dosing. Therefore, this study will be undertaken to assess the changes in pharmacodynamic measures of T cell activation using initially the dose regimen from CM4620-204, then the high dose regimen from CM4620-201, and then finally, a dose regimen with 5 days of Auxora infusion.

Results of the PD *ex vivo* blood assay of lymphocyte function in Study CM4620-202 indicated that when 2.08 mg/kg of Auxora was administered, at or near the C_{max}, CRAC channel-dependent stimulated IL-2 secretion was inhibited by approximately 57%. The inhibitory effect of Auxora dissipated over the next 1-2 days, demonstrating pharmacological reversal. This result suggests that long-term immunosuppression is unlikely to result from therapy with Auxora. Patients will be followed for 30 days to ensure that long term adverse events are collected.

2 OBJECTIVES AND ENDPOINTS

2.1 Primary Objective

- To assess the pharmacodynamic response of bronchoalveolar lavage (BAL) T cell/monocyte subsets and chemokine release to various doses of Auxora in patients with critical COVID-19 pneumonia

2.2 Secondary Objectives

- To assess the safety and tolerability of Auxora in patients with critical COVID-19 pneumonia
- To determine the serum and BAL pharmacokinetic profile of Auxora in patients with critical COVID-19 pneumonia

2.3 Endpoints

- Pharmacodynamic endpoint:
 - Proportion of immune cells in BAL fluid (specifically: Tregs, CD4 and CD8 T cells, B cells, NK cells, alveolar macrophages monocytes, and neutrophils). T cell activation will also be assessed via flow cytometry by assessing surface expression of HLA-DR and CD127.
 - Activation of all immune cell types will be assessed using integrative analysis of single cell RNA sequencing on all subjects across all time points. After demultiplexing reads will be aligned to a hybrid genome containing human (GRCh38) and SARS-CoV-2 (NC_045512.2) reference genomes. Resulting cell-by-gene matrices from all samples will be normalized using sctransform algorithm and integrated using BBKNN or scVI/scANVI approach followed by Leiden clustering, identification of marker genes for each cluster and assigning cell type identity to clusters (for details see [Grant et al., 2021](#)). It will be assessed whether treatment with Auxora resulted in emergence of the new clusters/cell types/cell states and markers characterizing these newly emergent populations will be evaluated. For homologous cell types differential genes expression analysis will be performed between Auxora- and placebo-treated subjects, split by time-points. The impact of Auxora treatment on detection of SARS-CoV-2 positive and negative strand RNA in infected cells will also be assessed. Differential gene expression will be performed on per-cluster level and using multilevel statistics (per-cluster and per subject level, to assess biological variability within the group).
- Efficacy endpoint
 - All-Cause Mortality at Day 60
 - Number of Days on Mechanical Ventilation after randomization
 - Number of Days in the Hospital after randomization
 - Number of Days in the ICU after randomization
- Safety endpoints
 - Pre-defined changes in cardiac conduction
 - The incidence of TEAEs and SAEs
 - The intensity and relationship of TEAEs and SAEs
 - Mortality at Day 30

3 INVESTIGATIONAL PLAN

3.1 Study Design

This will be a single-blind study where the patient will not know if they are receiving Auxora or Placebo. The first 4 patients will be enrolled in Cohort 1 and randomized 3:1 to Auxora or Placebo. If dose escalation occurs, the next 4 patients will be enrolled in Cohort 2 and randomized 3:1 to Auxora or Placebo. If dose escalation continues, the next 8 patients will be enrolled in Cohort 3 and randomized 3:1 to Auxora or Placebo. The decision to escalate dosing will be made by CalciMedica in consultation with the PI after the review of safety events in Cohorts 1 and 2.

Consultation between the PI and CalciMedica will occur if any patient receiving Auxora in Cohorts 1, 2 or 3 experiences one of the cardiac conduction events listed below during the 144 hours after the Start of the First Infusion of Study Drug (SFISD):

- QTcF interval of \geq 500 msec; or
- QTcF prolongation of \geq 60 msec as compared to baseline; or
- Mobitz Type II second degree atrioventricular (AV) block; or
- Third degree or high grade AV block; or
- Polymorphic Ventricular Tachycardia;

If one of the listed safety events occurs in a patient who is receiving Auxora in Cohort 1 but the event is not thought to be dose limiting, 4 additional patients will be enrolled in Cohort 1 and randomized 3:1 to Auxora versus Placebo for a total of 8 patients enrolled in the cohort, 6 randomized to Auxora and 2 to Placebo. The PI and CalciMedica will consult after all 8 patients are enrolled to determine if dose escalation to Cohort 2 will occur. If one of the listed safety events occurs in a patient who is receiving Auxora in Cohort 1 and the event is dose limiting, further dosing will not occur using the planned dose regimens but may occur using a regimen that provides lower total exposure of drug.

If one of the listed safety events occurs in a patient who is receiving Auxora in Cohort 2 but the event is not thought to be dose limiting, 4 additional patients will be enrolled in Cohort 2 and randomized 3:1 to Auxora versus Placebo. The PI and CalciMedica will consult after all patients are enrolled to determine if dose escalation to Cohort 3 will occur. If one of the listed safety events occurs in a patient who is receiving Auxora in Cohort 2 and the event is dose limiting, further dosing will not occur in either Cohorts 2 or 3. 4 additional patients may be enrolled in Cohort 1 and randomized 3:1 to Auxora versus Placebo. The 4 additional patients in Cohort 1 will receive a dose regimen of an initial infusion followed by continuous infusion for 48 hours.

If one of the listed safety events occurs in a patient who is receiving Auxora in Cohort 3 but the event is not felt to be dose limiting, 4 additional patients will be enrolled in Cohort 3 and randomized 3:1 to Auxora versus Placebo for a total of 12 patients enrolled in the cohort, 9 randomized to Auxora and 3 to Placebo. If one of the listed safety events occurs in a patient

who is receiving Auxora in Cohort 3 and the event is dose limiting, further dosing will not occur in Cohort 3. 4 additional patients may be enrolled in Cohort 2 and randomized 3:1 to Auxora versus Placebo. The 4 additional patients in Cohort 2 will receive a dose regimen of an initial infusion followed by continuous infusion for 72 hours.

A study physician or appropriately trained delegate will perform assessments at Screening, immediately prior to the SFISD, and then every 24 hours (± 1 hours) until 240 hours after the SFISD. After 240 hours from the SFISD, the patient will be assessed q48 hours until Day 30 after the SFISD, or until discharge if earlier. Patients who are discharged before Day 25 after the SFISD will be followed-up at Day 30 (± 5 days). Patients will be followed up at Day 60 (± 5 days) for a safety and mortality assessment. This assessment will be conducted by phone for patients discharged prior to Day 55. The Day 60 assessment will be completed as a final inpatient safety assessment for patients who remain hospitalized or are discharged from the hospital on Days 55-59.

Fluid from a bronchoalveolar lavage (BAL) should be obtained prior to the SFISD (-12 hours) and then again 24 (± 12) hours after the last infusion of study drug in Cohorts 1 and 2. In Cohort 3, BAL fluid will be obtained during the final 24 hours of the continuous infusion. BAL fluid will be used for flow cytometry, single cell RNA sequencing, and chemokine/biomarker panel. On the BAL fluid obtained from the second BAL, CM4620 levels will be determined in patients receiving Auxora.

ECGs will be performed and the QTcF will be recorded daily at each assessment until 144 (+2) hours from the SFISD. If at any time QT prolongation is suspected on a cardiac monitor, a ECG will be performed and a QTcF shall be recorded. Blood specimen for PK analysis should be obtained in patients receiving Auxora.

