	
• Third degree or high grade AV block; or• Polymorphic Ventricular Tachycardia; 
If one of the listed safety events occurs in a patient who is receiving Auxora in Cohort 1 but the event is not thought to be dose limiting, 4 additional patients will be enrolled in Cohort 1 and randomized 3:1 to Auxora versus Placebo for a total of 8 patients enrolled in the cohort, 6 randomized to Auxora and 2 to Placebo. The PI and CalciMedica will consult after all 8 patients are enrolled to determine if dose escalation to Cohort 2 will occur. If one of the listed safety events occurs in a patient who is receiving Auxora in Cohort 1 and the event is dose limiting, further dosing will not occur using the planned dose regimens but may occur using a regimen that provides lower total exposure of drug.
 
If one of the listed safety events occurs in a patient who is receiving Auxora in Cohort 2 but the event is not thought to be dose limiting, 4 additional patients will be enrolled in Cohort 2 and randomized 3:1 to Auxora versus Placebo for a total of 8 patients enrolled in the cohort, 6 randomized to Auxora and 2 to Placebo. The PI and CalciMedica will consult after all 8 patients are enrolled to determine if dose escalation to Cohort 3 will occur. If one of the listed safety events occurs in a patient who is receiving Auxora in Cohort 2 and the event is dose limiting, further dosing will not occur in either Cohorts 2 or 3. 4 additional patients may be enrolled in Cohort 1 and randomized 3:1 to Auxora versus Placebo. The 4 additional patients in Cohort 1 will receive a dose regimen of an initial infusion followed by continuous infusion for 48 hours.
 
If one of the listed safety events occurs in a patient who is receiving Auxora in Cohort 3 but the event is not felt to be dose limiting, 4 additional patients will be enrolled in Cohort 3 and randomized 3:1 to Auxora versus Placebo for a total of 12 patients enrolled in the cohort, 9 randomized to Auxora and 3 to Placebo. If one of the listed safety events occurs in a patient who is receiving Auxora in Cohort 3 and the event is dose limiting, further dosing will not occur in Cohort 3. 4 additional patients may be enrolled in Cohort 2 and randomized 3:1 to Auxora versus Placebo. The 4 additional patients in Cohort 2 will receive a dose regimen of an initial infusion followed by continuous infusion for 72 hours.
 
A study physician or appropriately trained delegate will perform assessments at Screening, immediately prior to the SFISD, and then every 24 hours (± 1 hours) until 240 hours after the SFISD. After 240 hours from the SFISD, the patient will be assessed q48 hours until Day 30 after the SFISD, or until discharge if earlier. Patients who are discharged before Day 25 after the SFISD will be followed-up at Day 30 (± 5 days). Patients will be followed up at Day 60 (± 5 days). for a safety and mortality assessment.

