#### Interim Analysis and Stopping Guidelines

As this is a dose-escalation study, Consultation between the PI and CalciMedica will occur if any patient receiving Auxora in Cohorts 1, 2 or 3 experiences one of the cardiac conduction events listed below during the 144 hours after the Start of the First Infusion of Study Drug (SFISD):

- QTcF interval of  $\geq$  500 msec; or
- QTcF prolongation of  $\geq$  60 msec as compared to baseline; or
- Mobitz Type II second degree atrioventricular (AV) block; or
- Third degree or high grade AV block; or
- Polymorphic Ventricular Tachycardia;

If one of the listed safety events occurs in a patient who is receiving Auxora in Cohort 1 but the event is not thought to be dose limiting, 4 additional patients will be enrolled in Cohort 1 and randomized 3:1 to Auxora versus Placebo for a total of 8 patients enrolled in the cohort, 6 randomized to Auxora and 2 to Placebo. The PI

and CalciMedica will consult after all 8 patients are enrolled to determine if dose escalation to Cohort 2 will occur. If one of the listed safety events occurs in a patient who is receiving Auxora in Cohort 1 and the event is dose limiting, further dosing will not occur using the planned dose regimens but may occur using a regimen that provides lower total exposure of drug.

If one of the listed safety events occurs in a patient who is receiving Auxora in Cohort 2 but the event is not thought to be dose limiting, 4 additional patients will be enrolled in Cohort 2 and randomized 3:1 to Auxora versus Placebo for a total of 12 patients enrolled in the cohort, 9 randomized to Auxora and 3 to Placebo. The PI and CalciMedica will consult after all 12 patients are enrolled to determine if dose escalation to Cohort 3 will occur. If one of the listed safety events occurs in a patient who is receiving Auxora in Cohort 2 and the event is dose limiting, further dosing will not occur in either Cohorts 2 or 3. 4 additional patients may be enrolled in Cohort 1 and randomized 3:1 to Auxora versus Placebo.

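### After a conduction signal, escalation from an expanded Cohort 1 or 2 may be decided once the last patient is enrolled, before the 144-hour conduction window is complete

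*Protocol*

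**What the plan says.** Section 3.1 of the Protocol requires the sponsor and the PI to consult if any Auxora patient "experiences one of the cardiac conduction events listed below during the 144 hours after the Start of the First Infusion of Study Drug". The list covers QTcF thresholds, high-degree AV block and polymorphic ventricular tachycardia. The follow-up matches the window: "ECGs will be performed and the QTcF will be recorded daily at each assessment until 144 (+2) hours from the SFISD".

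If such an event occurs in Cohort 1 or 2 and is judged not dose limiting, four further patients are randomized 3:1 in that cohort. The consultation on escalation is then timed as follows:

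- Cohort 1 (section 3.1): "The PI and CalciMedica will consult after all 8 patients are enrolled to determine if dose escalation to Cohort 2 will occur".
- Cohort 2 (section 3.1): "The PI and CalciMedica will consult after all patients are enrolled to determine if dose escalation to Cohort 3 will occur".
- Cohort 2 (Protocol synopsis, Study Design): "The PI and CalciMedica will consult after all 8 patients are enrolled to determine if dose escalation to Cohort 3 will occur".
- Cohort 2 (SAP, Interim Analysis and Stopping Guidelines): "The PI and CalciMedica will consult after all 12 patients are enrolled to determine if dose escalation to Cohort 3 will occur".

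The number of patients differs between these places, but the trigger is enrolment in each. The only other timing text is the general rule in section 3.1, under which the sponsor decides on escalation with the PI "after the review of safety events in Cohorts 1 and 2". It states no observation time.

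**The concern.** The expanded path exists because a conduction event has already been seen on Auxora. The four added patients are there to show whether it recurs, and their 144-hour windows are the new evidence. A trigger set at enrolment lets the decision be taken before that evidence is complete. For patients who arrive close together, it may be taken before most of the evidence exists.

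The later part of the window matters too. Dosing runs to about 52 h from SFISD in Cohort 1 (48 h plus a 4 h infusion) and about 76 h in Cohort 2 (72 h plus 4 h). The drug also accumulates: section 1.4.1 reports a 2.6-fold rise in 24-hour AUC from Day 1 to Day 7 of daily dosing. ECGs from the first day cannot stand in for the whole window.

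**Working it through.** The plan gives no minimum follow-up before escalation, so there is no figure of its own to reproduce on this point. Its one design figure, a half-width of 0.77 SD with 9 patients per arm, reproduces (2.306/√9 = 0.769) but has no bearing here.

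**Inputs.** Window 144 h from SFISD, with ECGs to 144 (+2) h (section 3.1). SFISD within 8 h of randomization (section 8.4). Second BAL at 72 ± 12 h in Cohort 1 and 96 ± 12 h in Cohort 2 (sections 8.7 and 8.8), or "then again 24 (± 12) hours after the last infusion of study drug in Cohorts 1 and 2" (section 3.1). Doses from the synopsis table.

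**1. Wait required.** As written, the wait after the last enrolment is 0 h. The last patient's window ends between 144 h (6.0 days) and 8 + 144 + 2 = 154 h (6.4 days) after randomization.

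**2. Added patients with incomplete windows at the earliest consultation.** The documents give no accrual rate, so equal gaps are assumed. Count k = 0, 1, 2, 3 with k × gap < 6 + 8/24 = 6.33 days (full 8 h lag), or < 6 days (no lag).

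| Assumed gap (days) | Incomplete of 4, 8 h lag | Incomplete of 4, no lag |
|---|---|---|
| 1 | 4 | 4 |
| 2 | 4 | 3 |
| 3 | 3 | 2 |
| 7 | 1 | 1 |

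If the four form one 3:1 block, the last 4, 3, 2 or 1 patients include 3, 2–3, 1–2 or 0–1 on Auxora. The count never falls below one patient, and that patient is on Auxora with probability 3/4.

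**3. Does the replacement rule close the gap?** Section 6.1 replaces patients who discontinue study drug, withdraw, are extubated or die before the second BAL. One could therefore say enrolment is final only at the last patient's second BAL. At nominal dosing times:

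- Cohort 1: BAL at 60–84 h, or 52 + 12 = 64 to 52 + 36 = 88 h. Left to run: 144 − 88 = 56 to 144 − 60 = 84 h (39–58% of the window), with 3–4 of the 6 daily ECGs to come.
- Cohort 2: BAL at 84–108 h, or 76 + 12 = 88 to 76 + 36 = 112 h. Left to run: 144 − 112 = 32 to 144 − 84 = 60 h (22–42%), with 2–3 of the 6 ECGs to come.

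The gap is smaller on this reading but remains.

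**4. When does the next cohort receive more drug?** Planned totals are 1.25 + 1 + 1 = 3.25, 1.25 + 1.25 + 1 + 1 = 4.5 and 1.25 + 4 × 1.0 = 5.25 mL/kg, so +38% and then +17%.

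- Cohort 1 to 2: Day 1 is identical and the excess begins with the 24 h dose. If Cohort 2 opened at once, the last Cohort 1 patient would then be about 24 − 8 = 16 to 24 h past SFISD.
- Cohort 2 to 3: at 28, 52 and 76 h the cumulative volume is 2.25, 3.25 and 4.25 mL/kg in Cohort 3, against 2.5, 3.5 and 4.5 in Cohort 2. Cohort 3 is ahead between Cohort 2's daily infusions, but passes Cohort 2's total only at 4 + 3.25 × 24 = 82 h. The last Cohort 2 patient would then be about 74–82 h past SFISD.

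**5. What complete windows are worth (illustration; event rates are assumed).** The chance of at least one event among m fully observed Auxora patients is 1 − (1 − p)^m. For p from 0.05 to 0.30 it is 14.3% to 65.7% with m = 3, 9.8% to 51.0% with m = 2, 5% to 30% with m = 1, and 0 with m = 0. Partly observed patients still contribute something, so these contrasts are upper limits on what is lost.

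**The case against.** The strongest reply is that the sentence sets an earliest time to confer and does not itself authorize escalation. The decision falls under the general rule on reviewing safety events, and a review of 144-hour events is most naturally a review of completed windows. That reading is reasonable, and the sponsor and PI are free to wait. But the general rule states no observation time, and the more specific sentence names enrolment, so nothing supplied requires the wait.

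The remaining safeguards are real:

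- Under section 3.1, a later dose-limiting event in Cohort 1 ends the planned regimens, and one in Cohort 2 ends dosing in Cohorts 2 and 3. Neither rule lapses when the next cohort opens.
- Daily ECGs and IDMC review continue, a suspected QT prolongation on the monitor prompts an extra ECG, and entry requires a QTcF of 440 ms or less.
- The Phase 1 studies showed no sustained QTcF effect in healthy subjects.
- Section 1.7 describes Cohort 2's regimen as the high-dose regimen of CM4620-201, so patients have had it before, although only 6 did and 4 of them did not receive all doses.
- The Safety Monitoring Plan and IDMC charter are not among the documents. Section 9.7 mentions only pause criteria for the plan, but either document may hold a waiting rule.

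These points limit the harm. They do not supply the missing evidence at the time of the decision, and the stopping rules act only after the next cohort may have opened.

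A reader might also infer that Cohort 2 to 3 is the most exposed step. The volume arithmetic does not support that: the excess over Cohort 2's total begins only at about 82 h, while Cohort 2 exceeds Cohort 1 from the 24 h dose. Volume is not plasma exposure, so this ranks the steps only roughly.

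**Conclusion.** The point holds as a defect in a stated trigger, confined to the expanded Cohort 1 and Cohort 2 paths. Followed as written, the plan lets escalation after a conduction signal be decided without the complete observation that the added patients were enrolled to provide. The firm part of its size is that 0 h of waiting is required, against 144 to 154 h for the last patient's window to finish. The counts of 1 to 4 incomplete patients rest on assumed accrual gaps, and the detection probabilities on assumed event rates.

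Two further inferences should be resisted. One is that escalation could precede any dosing of the last patient. That depends on an undefined word, enrolled, and on a lag of at most about 8 h from randomization; the unfinished window is the larger matter. The other is that a late event would go unanswered, which the written stopping rules contradict.

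The change should be made. Confidence is medium, because of the two unseen safety documents and because the path may never be entered.

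**What to change.** In the synopsis, section 3.1 and the SAP, replace the enrolment trigger in the expanded Cohort 1 and Cohort 2 sentences with: *after every Auxora-treated patient in the cohort has completed 144 hours from SFISD, or has died, withdrawn or been discharged earlier*. The discharge exception is needed because Appendix 2 schedules the daily assessments only for hospitalized patients. Adding the same condition to the general escalation sentence, for cohorts that are not expanded, is an optional clarification. If the Safety Monitoring Plan or IDMC charter already holds such a rule, a cross-reference in section 3.1 and the SAP would do.

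The cost is a protocol amendment under section 11.7, a matching SAP edit, and a wait of about 6.0 to 6.4 days after the last Auxora patient's randomization at each of at most two expanded-cohort escalations. A few eligible patients may be lost during the wait, since more than 7 days of ventilation excludes them (section 4.2).
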